**Biologic Sample Submission:**

Sample Type	Screening/Baseline	BKM120 alone phase (7-10 days)
Blood (whole blood with EDTA)	X	
Archived tumor	X	
Fresh Biopsy*	X	X

\*optional, but encouraged in patients with accessible tumors.

**11. MEASUREMENT OF EFFECT**

Although response is not the primary endpoint of this trial, participants with measurable disease will be assessed by standard criteria (RECIST 1.1)

[http://ctep.cancer.gov/protocolDevelopment/docs/Recist\\_Guideline.pdf](http://ctep.cancer.gov/protocolDevelopment/docs/Recist_Guideline.pdf)

**12. DATA REPORTING / REGULATORY REQUIREMENTS**

Adverse event lists, guidelines, and instructions for AE reporting can be found in Section 7.0 (Adverse Events: List and Reporting Requirements).

**12.1 Data Reporting**

The QACT will collect, manage, and perform quality checks on the data for this study.

## 12.2 Data Safety Monitoring

The DF/HCC Data and Safety Monitoring Committee (DSMC) will review and monitor toxicity and accrual data from this study. The committee is composed of clinical specialists with experience in oncology and who have no direct relationship with the study. Information that raises any questions about participant safety will be addressed with the Overall PI and study team.

The DSMC will review each protocol up to four times a year or more often if required to review toxicity and accrual data. Information to be provided to the committee may include: up-to-date participant accrual; current dose level information; DLT information; all grade 2 or higher unexpected adverse events that have been reported; summary of all deaths occurring within 30 days of intervention for Phase I or II protocols; for gene therapy protocols, summary of all deaths while being treated and during active follow-up; any response information; audit results, and a summary provided by the study team. Other information (e.g. scans, laboratory values) will be provided upon request.

## 13. STATISTICAL CONSIDERATIONS

This trial follows a standard 3+3 phase I design. The primary endpoint is to determine the MTD. Patients will be started at a given dose and escalated according to the information outlined in section 5.3. The table below gives the probabilities of the dose escalation scheme outlined in section 5.3.

True Rate of DLT	Probability of Escalation
20%	.71
30%	.49
40%	.31
50%	.17
60%	.08

For example, if the true rate of DLT is 20% at a given dose, there is a 71% probability of escalating to a higher dose.

At most, 46 patients are estimated to be accrued. This is based on studying 6 levels of BKM120+Cisplatin (section 5.3) with at most 6 patients per level plus an additional 10 at the MTD (these 10 accrued to ensure that the adverse event rate at the MTD is acceptable). The estimation of adverse events will be based on studying these 10 additional patients. The width of the 90% confidence interval for the estimation of the adverse event rate will be no more than 56%. The monthly accrual rate is estimated to be 2 to 3 patients.

For secondary objectives: best overall response rate will be summarized as a proportion with a corresponding 90% exact confidence interval, the distributions of progression and survival will be estimated using a Kaplan-Meier method with corresponding 90% confidence intervals for the median or time-specific event time, scores from the GAD-7 and the PHQ-9 to assess mood will be summarized across the timepoints of assessment. Several correlative studies are planned to learn more about how BKM120 blocks PIK. NexGen sequencing of the specimens and studies to investigate the influence of the NFE2L2/KEAP1/CUL3 are planned (see sections 9.1 and Appendix D). Given the small sample size of this trial, these studies are exploratory.

## 14. PUBLICATION PLAN

The results will be made public within 24 months of the end of data collection. A report is planned to be published in a peer-reviewed journal and that initial release may be an abstract that meets the requirements of the International Committee of Medical Journal Editors. A full report of the outcomes will be made public no later than three years after the end of data collection.

**16. APPENDICES**

**APPENDIX A: PERFORMANCE STATUS CRITERIA**

ECOG Performance Status Scale		Karnofsky Performance Scale	
Grade	Descriptions	Percent	Description
0	Normal activity. Fully active, able to carry on all pre-disease performance without restriction.	100	Normal, no complaints, no evidence of disease.
		90	Able to carry on normal activity; minor signs or symptoms of disease.
1	Symptoms, but ambulatory. Restricted in physically strenuous activity, but ambulatory and able to carry out work of a light or sedentary nature (e.g., light housework, office work).	80	Normal activity with effort; some signs or symptoms of disease.
		70	Cares for self, unable to carry on normal activity or to do active work.
2	In bed <50% of the time. Ambulatory and capable of all self-care, but unable to carry out any work activities. Up and about more than 50% of waking hours.	60	Requires occasional assistance, but is able to care for most of his/her needs.
		50	Requires considerable assistance and frequent medical care.
3	In bed >50% of the time. Capable of only limited self-care, confined to bed or chair more than 50% of waking hours.	40	Disabled, requires special care and assistance.
		30	Severely disabled, hospitalization indicated. Death not imminent.
4	100% bedridden. Completely disabled. Cannot carry on any self-care. Totally confined to bed or chair.	20	Very sick, hospitalization indicated. Death not imminent.
		10	Moribund, fatal processes progressing rapidly.
5	Dead.	0	Dead.

## APPENDIX B: DRUGS THAT ARE PROHIBITED

- Other investigational therapies must not be used while the patient is on the study.
- Anticancer therapy (chemotherapy, biologic or radiation therapy, and surgery) other than the study treatments must not be given to patients while the patient is on the study. If such agents are required for a patient then the patient must be discontinued from the study.
- In *vitro* metabolism studies suggest that oxidative metabolism of BKM120 is predominantly mediated by CYP3A4 (fm>0.9), with only minor contributions of CYP1A1. As BKM120 is a sensitive CYP3A4 substrate, co-administration of BKM120 with strong and moderate CYP3A4 inhibitors and CYP3A4 inducers is prohibited. See below for a list of prohibited drugs. Please note this list may not be comprehensive.
- Based on in vitro studies, co-administration of BKM120 with CYP3A4 inducers is predicted to decrease the systemic exposure to BKM120, thereby increasing the risk of exposing the patient to subtherapeutic drug levels. See below for a list of prohibited CYP3A inducers. Please note that this list may not be comprehensive. Therapeutic doses of warfarin sodium (Coumadin®) or any other coumadin-derivative anticoagulants are not permitted.
- If a patient requires the concomitant use of any medication included in Table 18 below entitled “List of Prohibited QT prolonging drugs” (i.e., drugs that are generally accepted by the Qtdrugs.org Advisory Board of the Arizona CERT to have a risk of causing Torsades des de Pointes), study treatment administration must be interrupted as long as the patient requires therapy with the QT prolonging agent.
- Herbal preparations/medications are not allowed throughout the study. These herbal medications include, but are not limited to St. John’s wort, Kava, ephedra (ma huang), ginko biloba, dehydroepiandrosterone (DHEA), yohimbe, saw palmetto, ginseng. Patients should stop using these herbal medications 7 days prior to first dose of study drug.
- Hormonal contraceptives may be affected by cytochrome P450 interactions, and are therefore not considered effective in this study.

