## 5.6 Follow-up for dose-limiting toxicities

Patients whose treatment is interrupted or permanently discontinued due to an adverse event or clinically significant laboratory value, must be followed as outlined in Table 10, at least once a week for 4 weeks, and subsequently at 4-week intervals, until resolution or stabilization of the event, whichever comes first. If a patient requires a dose delay of > 14 days from the intended day of the next scheduled dose, then the patient should be discontinued from the treatment but will only come off study if dead or due to refusal to continue on the study. All patients must be followed for adverse events and serious adverse events for 28 days following the last dose of BKM120.

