## **5.7 Monitoring of BKM120 suspected toxicities**

Patients whose treatment is interrupted or permanently discontinued due to an adverse event or clinically significant laboratory value, must be followed as outlined in Table 10, at least once a week for 4 weeks, and subsequently at 4-week intervals, until resolution or stabilization of the event, whichever comes first. If a patient requires a dose delay of > 14 days from the intended day of the next scheduled dose, then the patient should be discontinued from study treatment. If the patient requires more than 2 dose reductions, the patient should be discontinued from study treatment. All patients must be followed for adverse events and serious adverse events for 28 days following the last dose of BKM120. All SAEs must be reported to Novartis as detailed in section 5.12.11 and 5.12.12.

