## **5.8 Agent Administration**

### **5.8.1 BKM120 Administration**

The study drug BKM120 will be self-administered (by the patients themselves). The investigator will instruct the patient to take the study drug exactly as specified in the protocol. BKM120 will be administered on a continuous once daily dosing schedule. Patients should be instructed to take the dose of BKM120 daily in the morning, one hour after a light breakfast (morning meal) at approximately the same time each day. BKM120 should be taken with a glass of water and consumed over as short a time as possible. Patients should swallow the capsules as a whole and not chew them. Do not crush capsule. Patients should continue to fast for 2 hours after the administration of each BKM120 dose.

If vomiting occurs during the course of treatment, no re-dosing of the patient is allowed before the next scheduled dose. The occurrence and frequency of any vomiting during a treatment must be noted as an adverse event. In addition, on the days of full pharmacokinetic sampling, the exact time of any episodes of vomiting within the first 4 hours post-dosing on that day and within the first 4 hours following the previous day's dosing must be noted whenever possible.

If the patient forgets to take her/his dose AFTER 6:00 PM, then the dose should be withheld that day and BKM120 should be restarted the following day.

Patients must avoid consumption of St. John's Wort, Seville oranges, grapefruit or grapefruit juice, grapefruit hybrids, pummelos and exotic citrus fruits from 7 days prior to the first dose of study medication and during the entire study treatment period due to potential CYP3A4 interaction with the study medication. Patients must avoid concomitant intake of strong and moderate CYP3A4/5 inhibitors and inducers. Orange juice is allowed.

All dosages prescribed and dispensed to the patient and all dose changes during the study must be recorded. If a patient requires a BKM120 dose delay of >14days from the previous dose, the patient must be discontinued from treatment but will only come off study if dead or due to refusal to continue on the study. Patients will only require a 28 day follow up visit after the last dose of BKM120.

Medication labels will comply with US legal requirements and be printed in English. They will supply no information about the patient. The storage conditions for study drug will be described on the medication label.

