Grade 3	
Omit dose until resolved to <math>\leq</math> Grade 1, then <math>\downarrow</math> 1 dose level (co-medicate)
 
Note: If question 9 on the PHQ-9 has a positive response, or worsens in severity, the patient should be referred for psychiatric consult regardless of the total questionnaire score

Grade 4	
Omit dose and discontinue patient from study
 
Note: If question 9 on the PHQ-9 has a positive response, or worsens in severity, the patient should be referred for psychiatric consult regardless of the total questionnaire score

Rash	
Grade 1	Maintain dose level. Consider to initiate appropriate skin toxicity therapy (such as antihistamines, topical corticosteroids)
Grade 2	Maintain dose level. Initiate/intensify appropriate skin toxicity therapy (such as antihistamines, topical corticosteroids)
Grade 3	
Omit dose until resolved to CTCAE Grade <math>\leq</math> 1, then:
 
 
If resolved in <math>\leq</math> 7 days, <math>\downarrow</math> 1 dose level
 
If resolved in <math>></math> 7 days (despite appropriate skin toxicity therapy), discontinue patient from BKM120
 

Grade 4	Omit dose and discontinue patient from BKM120
Fatigue (asthenia)	
Grade 1 or 2	Maintain dose level
Grade 3	
Omit dose until resolved to <math>\leq</math> Grade 1, then:
 
 
If resolved in <math>\leq</math> 7 days, maintain dose level
 
If resolved in <math>></math> 7 days, <math>\downarrow</math> 1 dose level
 

Grade 4	Omit dose and discontinue patient from BKM120
Other non-hematological adverse events	
Grade 1 or 2	Maintain dose level
Grade 3	Omit dose until resolved to $\leq$ Grade 1, then $\downarrow$ 1 dose level
Grade 4	
Omit dose and discontinue patient from study
 
Note: Omit dose for <math>\geq</math> Grade 3 vomiting or Grade 3 nausea only if the vomiting or nausea cannot be controlled with optimal antiemetic

Pneumonitis	See Table 15
** Common Terminology Criteria for Adverse Events (CTCAE) version 4.0.	

Fasting Plasma Glucose (FPG)	

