### 7.1.1.4 Management of Hyperglycemia

In addition to the dose modification and hyperglycemia treatment guidelines in Table 5.

- Under the supervision of an endocrinologist, an insulin regimen should be initiated according to institutional standard of care or the Treat-To-Target Algorithm for Lantus® (Riddle, Rosenstock, and Gerich 2003).
- For any hyperglycemia  $\geq$  grade 1, the patient should continue to follow dietary guidelines provided by the American Diabetes Association (American Diabetes Association 2004).
- For each patient, a maximum of 2 dose reductions will be allowed after which the patient should be discontinued from the study. In addition, a patient must discontinue treatment with BKM120, if after treatment is resumed at a lower dose, hyperglycemia recurs at a worse severity.
- For each patient, once a dose level reduction has occurred, the dose level may not be re-escalated in that patient during future treatment with BKM120.
- Based upon the results of preliminary clinical data and actual laboratory values (e.g., glucose, insulin) generated, the treatment recommendations for study drug induced hyperglycemia may be modified as needed.

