 Serum chemistry - K+, Na+, Ca++, Mg++, LDH, ALT, AST, total bilirubin (direct and indirect), creatinine, amylase, GGT, lipase, alkaline phosphatase (fractionated if alkaline phosphatase is grade 2 or higher), bicarbonate, phosphorus, uric acid, total cholesterol, HDL, LDL, triglycerides, glucose, urea or BUN, albumin, and total protein are required at baseline and at end of treatment. Subsequent assessments always include K+, Na+, Mg++, Ca++, ALT, AST, total bilirubin (direct and indirect), creatinine, alkaline phosphatase, bicarbonate, phosphorus, glucose, urea or BUN, albumin, and total protein BUT, lipase, total cholesterol, HDL, LDL, triglycerides should be obtained on Day 1 of CRT and EOT  Coagulation - PT or INR, PTT: Day 1 of CRT and EOT

 Patients must be fasting overnight for at least 8 hours. Additional measurements may be performed as clinically indicated.

 Patients will be assessed weekly for adverse events for the duration of the treatment (2 weeks of BKM120 and 7 weeks of BKM120+CRT = 9 weeks) and every 2 weeks after conclusion of BKM120+CRT (EOT) during the first month, then monthly for 3 months, then every 3 months, until first progression, death, or 2 years post study entry whichever occurs first.

 Follow up (FU) will take place every 2 weeks after conclusion of BKM120+CRT (EOT) during the first month, then monthly for 3 months, then every 3 months, until first progression, death, or 2 years post study entry whichever occurs first. Follow up visits must occur within +/- 14 days of the protocol specified date.

 After first progression, patients will be followed for survival every 3 months until 2 years post study entry.

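### Off-study wording for new anticancer therapy and toxicity conflicts with the planned 2-year follow-up and, if sites apply it literally, could censor overall survival informatively

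*Combined protocol and SAP*

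**What the plan says.** Four places can be read as ending participation or follow-up.

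- Appendix B, on anticancer treatment outside the protocol, surgery included: "If such agents are required for a patient then the patient must be discontinued from the study".
- Table 11, for grade 4 mood alteration and for grade 4 other non-hematological events: "Omit dose and discontinue patient from study".
- Section 7.1.1.4, on hyperglycemia: "a maximum of 2 dose reductions will be allowed after which the patient should be discontinued from the study".
- Section 5.8.1, in the paragraph on BKM120 delays over 14 days: "Patients will only require a 28 day follow up visit after the last dose of BKM120".

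Other places keep patients in follow-up.

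- Section 5.6, for a delay over 14 days, says the patient stops treatment but "will only come off study if dead or due to refusal to continue on the study".
- Section 5.8.1, in the sentence just before the 28-day one: "the patient must be discontinued from treatment but will only come off study if dead or due to refusal to continue on the study".
- Section 5.7: "If the patient requires more than 2 dose reductions, the patient should be discontinued from study treatment".
- Section 5.13 and Table 17 footnote 10 run follow-up visits to first progression, death or 2 years.
- Table 17 footnote 11: "After first progression, patients will be followed for survival every 3 months until 2 years post study entry".

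Section 5.12.8 censors overall survival (OS) at the last date the patient was known to be alive, and time to progression (TTP) at the last date known to be free of progression. Section 13 estimates both by Kaplan-Meier with 90% confidence intervals. It has no rule for patients who leave the study or start new therapy.

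**The concern.** These are stated rules that disagree, so a site can follow one only by breaking another. The patients caught by the Appendix B rule are largely those whose disease has come back. If such a patient is recorded as off study when salvage therapy is needed, and nobody collects vital status afterwards, the last date known alive falls near recurrence. The later death is never counted. Kaplan-Meier assumes that censored patients have the same outlook as those still at risk, and here they would do worse, so the OS curve would sit too high.

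TTP and survival are named secondary objectives, and Section 1.1 says the trial is also meant to give preliminary efficacy information. With at most 46 patients, a few uncounted deaths would show in the curve.

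**Working it through.** **1. Is the wording loose, or does the protocol mean two different things?** Section 5.14 is headed as covering removal from treatment and/or from the study itself, and it asks for one form when treatment ends and another when the patient comes off study. In Table 11, grade 4 rash and grade 4 fatigue lead to discontinuation from BKM120, while grade 4 mood events lead to discontinuation from the study. The protocol therefore uses the two terms as distinct, and a site may take the off-study wording at face value.

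**2. Is the Appendix B rule limited to the treatment period?** Its text ties the ban to being on the study, which under footnotes 10 and 11 can last 2 years. Elsewhere in the same appendix, the Table 18 ban on QT-prolonging drugs is expressly limited to the time until study treatment is permanently discontinued. The anticancer bullet has no such limit.

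**3. Dose-reduction limit.** Section 5.7 takes the patient off study treatment if more than 2 reductions are needed. Section 7.1.1.4 allows at most 2, after which the patient leaves the study. Both the trigger wording and the consequence differ.

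**4. Reach of the 28-day reading.** A patient who took BKM120 for the full 9 weeks would be seen until week 9 + 4 = 13. The one scheduled response scan, 3 months after chemoradiotherapy, falls at about week 9 + 13 = 22, and 2 years is week 104. A patient who stopped earlier would be lost earlier still. Read as the whole of follow-up, the sentence leaves almost no TTP or OS information.

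**5. Size of the OS effect (illustration).** The plan states no TTP or OS target, event count or power, so there is no planned figure to reproduce for these endpoints. Its maximum accrual does reproduce: 6 × 6 + 10 = 46. Section 2.1 puts the historical cure rate at about 50%. All other inputs are assumed:

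- F = progression by 24 months, giving a progression hazard λ = −ln(1 − F)/24;
- 5% death without progression by 24 months, h = −ln(0.95)/24;
- m = median survival after progression in months, μ = ln 2/m;
- q = share of progressors taken off study and no longer followed.

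Let P0(t) be the probability of being alive without progression and P1(t) alive after progression. Then P0(t) = exp(−at) with a = λ + h, and P1(t) = λ[exp(−at) − exp(−μt)]/(μ − a). True 24-month OS is P0(24) + P1(24). If removal happens at progression, Kaplan-Meier converges to exp(−∫H(t)dt) over 0 to 24 months, where H = [hP0 + μ(1 − q)P1]/[P0 + (1 − q)P1].

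Worked case, F = 50%, m = 9, q = 1: λ = 0.0289, h = 0.0021, a = 0.0310, μ = 0.0770. P0(24) = 0.5 × 0.95 = 0.475. P1(24) = 0.0289 × (0.475 − 0.1575)/0.0460 = 0.199. True OS is 0.674. Kaplan-Meier sees only deaths without progression and gives 0.950, an excess of 28 points.

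| Share of progressors lost | F 30%, m 18: true → Kaplan-Meier | F 50%, m 9: true → Kaplan-Meier | Excess (points) |
|---|---|---|---|
| 25% | 0.850 → 0.871 | 0.674 → 0.723 | 2 to 5 |
| 50% | 0.850 → 0.894 | 0.674 → 0.783 | 4 to 11 |
| 100% | 0.850 → 0.950 | 0.674 → 0.950 | 10 to 28 |

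A second set, with removal one month after progression, F = 40-50% and m = 6-12, gives excesses of 3-5, 7-11 and 16-27 points for the same three shares.

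**6. Toxicity removals.** Assume that 10-30% of patients are lost at month 3, that 24-month OS is 70% in the rest, and that r is the hazard ratio for death in those lost. True OS is (1 − g) × 0.70 + g × 0.70^r, where g is the share lost. For g = 30% and r = 2 it is 0.490 + 0.3 × 0.490 = 0.637 against a Kaplan-Meier value of 0.690, which is 5 points too high. For r = 1 there is no bias. For g = 30% and r = 0.75, true OS is 0.719 against 0.702, which is 2 points too low. The documents do not give r.

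**7. TTP.** Salvage therapy after documented progression cannot censor TTP, because the event has already been counted. Only removal before progression can: toxicity, the 28-day reading, or new therapy or surgery without documented progression.

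**The case against.** The main scenario is already addressed. Footnote 11 requires survival contact every 3 months after progression, and Table 17 has a column for it. Section 5.10 cites Appendix B as the list of exceptions to permitted concomitant treatment. If that appendix ended survival follow-up at salvage, footnote 11 would have little left to do, because progressors are the patients most likely to need new therapy. Section 5.12.8 censors at the last date known alive, not at the off-study date. The 28-day sentence follows directly on one that keeps such patients on study, and Sections 5.6 and 5.7 use 28 days as the adverse-event window, so it plausibly means the safety visit.

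Most of this stands, and it makes the bias conditional. A reader might infer that the plan censors patients at salvage therapy, so that survival will be overstated. The documents do not support that: it happens only if sites apply the off-study wording and also stop collecting status, against footnote 11. Nor do they support carrying the claim over to TTP at salvage, or a fixed upward bias from toxicity removals. The 28-point figure needs every progressor to be lost.

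The objection does not remove the conflict. Section 5.14 separates the two kinds of removal in its heading and forms, but then gives one shared list of reasons without saying which end treatment and which end follow-up. The protocol does not say which text prevails.

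**Conclusion.** The inconsistency is established from the text. Appendix B, Table 11 and Section 7.1.1.4, and on one reading 5.8.1, cannot all be followed together with 5.6, 5.7, 5.13 and Table 17 footnotes 10 and 11. The effect on OS is a risk, not a certainty. If sites stop collecting status at salvage therapy, 2-year OS could be overstated by about 2-5 points with a quarter of progressors lost and 4-11 with half lost. Only complete loss reaches 10-28. These figures rest on the assumed progression rates, post-progression survival and shares lost shown above.

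For TTP the exposure is limited to removal before documented progression and is not quantified here. For toxicity removals the direction of bias is unknown.

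TTP and OS are secondary and descriptive in a single-arm trial, with no target or comparison. The MTD is not affected by this censoring. The point should be corrected because doing so is cheap, but it does not threaten the primary objective.

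**What to change.** Reconcile Appendix B, Table 11, Section 7.1.1.4 and Section 5.8.1 with Sections 5.6, 5.7 and 5.13 and Table 17 footnotes 10 and 11, so that:

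- stopping study treatment, or starting other anticancer therapy, does not end follow-up for progression and survival, which continues as in footnotes 10 and 11 unless the patient refuses;
- the 28-day visit in 5.8.1 is described as the minimum safety visit and does not replace outcome follow-up;
- Section 5.12.8 says that OS is not censored at new anticancer therapy or at the end of treatment.

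The different dose-reduction limits in Sections 5.7 and 7.1.1.4 must also be reconciled. Which limit applies is a clinical decision for the sponsor and is not judged here.

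The cost is an amendment to wording. No treatment-stopping trigger changes, and the 3-monthly survival contacts are already planned.
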